Given its clinical significance, NRM at Month 6 will be assessed as the key secondary endpoint. Based on MacMillan et al (2015), the overall NRM at Month 6 in the BAT arm is 33%, with a stratum-specific NRM of 22% for standard risk and 44% for high risk (assuming a standard risk:high risk ratio of 0.50:0.50). A 40% relative reduction in NRM rate will be considered a clinically meaningful improvement. A sample size of 414 subjects (207 subjects per treatment cohort) will provide 83% power to detect a relative reduction of 40% (or absolute difference of 13.2%, ie, 19.8% vs 33% at Day 180) between treatment cohorts at a 1-sided  $\alpha$  level of 0.025 with an odds ratio of 0.50. A CMH test with 2-strata will be used. Stratum-specific NRM rates of 12.4% and 28.2% are expected for standard-risk and high-risk cohorts, respectively. Power for the CMH test with stratification based on GVHD risk score was calculated using software N-Query 5.0.

In order to compensate for an anticipated early withdrawal rate of up to 5% (ie, subjects who do not have any response data before Day 28), a total of 436 subjects (218 per treatment arm) will be randomized into the study to ensure a sample size of 414 evaluable subjects.

If the Day 180 NRM rate difference between 2 groups is tested using a Kaplan–Meier estimator of the cumulative distribution function at Day 180, with the rates being 19.8% and 33%, respectively, simulations (with sample size of 436 subjects) have shown that the power of detecting treatment difference is 0.811.

### 9.2.1. Interim Analysis 1

The first interim analysis for futility only will be performed when 112 subjects (25.7% of the planned 436 subjects) have completed the Day 28 visit or withdrew early from the study. No alpha will be spent during the first interim analysis. The stopping rule is nonbinding. When the conditional power is <20%, the sponsor may consider terminating the study if the totality of evidence is warranted. The conditional power is calculated assuming that the estimated treatment effect at the interim analysis is the true effect using the following formula (Jennison and Turnbull 2000):

$$\Phi\left(\frac{z}{\sqrt{t(1-t)}} - \frac{z_{\alpha/2}}{\sqrt{1-t}}\right)$$

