#### 9.4.2. Secondary Analyses

The key secondary endpoint is NRM at Month 6, defined as the proportion of subjects who died due to causes other than malignancy relapse at Month 6. The comparison of NRM at Month 6 between treatment cohorts will be conducted using a 2-sample proportion test with normal approximation. Summary statistics and 95% CI will be provided.

Additional secondary endpoints will be analyzed as follows:

- ORR, defined as the proportion of subjects demonstrating a CR, VGPR, or PR at Days 14, 56, and 100. The comparison between treatment cohorts will be conducted using a 2-sample proportion test with normal approximation. Summary statistics and applicable 95% CI will be provided.
- NRM, defined as the proportion of subjects who died due to causes other than malignancy relapse at Months 9, 12, and 24. The comparison between treatment cohorts will be conducted using a 2-sample proportion test with normal approximation. Cumulative incidence rates will be provided. Summary statistics and applicable 95% CI will be provided.
- DOR, defined as the time from first response until GVHD progression or death. The comparison between treatment cohorts will be conducted using the log-rank test. The Kaplan-Meier method will be used. Summary statistics will be provided.
- TTR, defined as the interval from treatment initiation to first response.
- Relapse rate of malignant and nonmalignant hematologic diseases, defined as the proportion of subjects whose underlying disease relapses. The comparison between treatment cohorts will be conducted using a 2-sample proportion test with normal approximation. The cumulative incidence rate and summary statistics will be provided.

- Relapse-related mortality rate, defined as the proportion of subjects whose malignancy relapses and has a fatal outcome. The comparison between treatment cohorts will be conducted using a 2-sample proportion test with normal approximation. The cumulative incidence rate and summary statistics will be provided.
- FFS, defined as the proportion of subjects who are still alive, have not relapsed, have not required additional therapy for aGVHD, and have not demonstrated signs or symptoms of cGVHD, at Month 6. The comparison between treatment cohorts will be conducted using the log-rank test. The Kaplan-Meier method will be used. Summary statistics will be provided.

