3.3. Sample Size Considerations

A sample size of 414 subjects with 1:1 randomization (itacitinib vs placebo) and stratification based on baseline aGVHD risk status (standard risk vs high risk) provides approximately 90% power to test for the primary endpoint (ORR at Day 28) and approximately 80% power to test for the key secondary endpoint (NRM rate at Month 6). The family-wise α -level will be controlled at 0.025 overall for the two comparisons. Specifically, this study will claim to have achieved the efficacy objective when the primary endpoint ORR at Day 28 shows a significant treatment effect at 1-sided $\alpha = 0.025$. Conditional on significance of the primary endpoint, the key secondary endpoint (NRM rate at Month 6) will be tested at 1-sided $\alpha = 0.025$.

An absolute improvement of 16% in the primary endpoint of ORR at Day 28 would be considered a clinically meaningful improvement over standard first-line systemic treatment for aGVHD. A sample size of 414 subjects (207 subjects per treatment group) will provide approximately 90% power to detect a 16% overall difference (72% vs 56%) between treatment groups for the primary endpoint (ORR at Day 28) at a 1-sided alpha level of 0.025.

The assumed Day 28 ORR of 56% is based on MacMillan et al (2015). The stratum-specific response rates (standard risk, 68%; high risk, 44%) assume a standard risk:high risk ratio of 0.50:0.50. It is expected that treatment with itacitinib will result in a 16% increase in the ORR, that is, an expected odds ratio of 2.02 (which corresponds to an overall increase in ORR to 72%), with stratum-specific response rates of 81% and 61% for standard-risk and high-risk aGVHD cohorts, respectively. Power for the CMH test with stratification based on GVHD risk score was calculated using software N-Query 5.0.

[figure not shown]

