Given its clinical significance, NRM rate at Month 6 will be assessed as the key secondary endpoint. The Day 180 NRM rate difference between 2 groups is tested using a KM estimator of the cumulative distribution function at Day 180. Based on MacMillan et al (2015), the overall NRM at Month 6 in the best available therapy group is 33%, with a stratum-specific NRM rate of 22% for standard risk and 44% for high risk (assuming a standard risk:high risk ratio of 0.50:0.50). A 40% relative reduction in NRM rate will be considered a clinically meaningful improvement. Based on simulation, a sample size of 414 subjects (207 subjects per treatment cohort) will provide approximately 80% power to detect a relative reduction of 40% (or absolute difference of 13.2%, ie, 19.8% vs 33% at Day 180) between treatments at a 1-sided α level of 0.025. NRM at Month 6 will be tested using a CMH test stratified by risk status (standard-risk vs high-risk aGVHD). Stratum-specific NRM rates of 12.4% and 28.2% are expected for standard-risk and high-risk cohorts, respectively. Power for the CMH test with stratification based on GVHD risk score was calculated using software N-Query 5.0.

In order to compensate for an anticipated early withdrawal rate of up to 5% (ie, subjects who do not have any response data before Day 28), a total of 436 subjects (218 per treatment arm) will be randomized into the study to ensure a sample size of 414 evaluable subjects.

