The first interim analysis for futility only will be performed when 112 subjects (25.7% of the planned 436 subjects) have completed the Day 28 visit or withdrew early from study. No alpha will be spent during the first interim analysis. The stopping rule is nonbinding. When the conditional power is < 20%, the sponsor may consider terminating the study if the totality of evidence is warranted. The conditional power is calculated assuming that the estimated treatment effect at the interim analysis is the true effect using the formula (Jennison and Turnbull 1999):

$$\Phi \left(\frac{z}{\sqrt{t(1-t)}} - \frac{z_{\alpha/2}}{\sqrt{1-t}} \right)$$

where Φ is the cumulative distribution function of the observed normalized test statistic z , and t is the information fraction (ie, observed sample at interim divided by the planned total sample size 436); $t = 0.257$ at Interim 1 and $z_{\alpha/2} = 1.96$.

Since CMH test with only 1 stratification factor, aGVHD risk status (standard vs high risk), will be used to test ORR at Day 28, it is thus a chi-square test with degree of freedom equal to 1, that is, $\chi^2_{df=1}$. Taking the square root of the observed CMH test statistic $\chi^2_{df=1}$ will result in normalized test statistic z .

3.4.2. Interim Analysis 2

For Interim Analysis 2, the analysis of both efficacy and futility will use a clinical database cutoff based on when 240 eligible subjects (55.0% of the targeted 436 subjects) have completed the Day 180 visit or withdrew from the study prior to Day 180.

The Hwang-Shih-DeCani alpha spending function with shape parameter -4 (O'Brian-Fleming like boundary) will be used to define upper efficacy boundary for the primary analysis of ORR at Day 28 when approximately 240 eligible subjects reach Day 180 (Hwang et al 1990). Based on enrollment projection, there will be approximately 360 subjects who have completed Day 28.

Table 2 lists efficacy boundary when information fraction (ie, the percentage of subjects) is 0.826 (360 subjects complete Day 28) at Interim 2; if ORR tested at Day 28 crosses the boundary, then the key secondary endpoint, 6-month NRM rate, will be tested by using the Bonferroni method for alpha spending (ie, 0.0125 as compared with 1-sided p-value at both interim and final analyses). By simulation, without considering early stopping for futility, the power of testing 6-month NRM at Interim 2 (with 240 eligible subjects who have completed Day 180) is approximately 0.608.

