7.4.1.1. Primary Analysis of Nonrelapse Mortality Rate at Month 6 (Day 180)

For the primary analysis, NRM will be analyzed using a stratified CMH test. Month 6 NRM will be summarized using descriptive statistics by treatment group with 2-sided exact binomial 95% CIs. P-value, mean proportion difference, odds ratio, and 95% Wald confidence limits calculated from stratified CMH test will also be presented.

Let $\hat{p}_{pbo,i}$ be the estimated proportion of evaluable subjects in the placebo group in stratum i who died due to causes other than malignancy relapse prior to or on Day 180 (ie, excluding those subjects who are either ongoing and have not reached Day 180, who withdrew from study prior to Day 180, or who died due to relapse) with corresponding variance estimator $\hat{V}(\hat{p}_{pbo,i})$. Let $\hat{p}_{trt,i}$ and $\hat{V}(\hat{p}_{trt,i})$ be the same for the itacitinib group in stratum i .

The overall estimate of treatment difference in Day 180 NRM between placebo and itacitinib is defined as the following:

$$w * [\hat{p}_{pbo,standard} - \hat{p}_{trt,standard}] + (1 - w) * [\hat{p}_{pbo,high} - \hat{p}_{trt,high}]$$

Its 95% CI is the above estimate of difference

$$\pm 1.96 * \text{sqrt} (w^2 * (\hat{V}(\hat{p}_{pbo,standard}) + \hat{V}(\hat{p}_{trt,standard})) + (1 - w)^2 * (\hat{V}(\hat{p}_{pbo,high}) + \hat{V}(\hat{p}_{trt,high})))$$

With weight w defined by inverse of variance in 2 baseline GVHD risk groups. That is:

$$w = \frac{1/[\hat{V}(\hat{p}_{pbo,standard}) + \hat{V}(\hat{p}_{trt,standard})]}{1/[\hat{V}(\hat{p}_{pbo,standard}) + \hat{V}(\hat{p}_{trt,standard})] + 1/[\hat{V}(\hat{p}_{pbo,high}) + \hat{V}(\hat{p}_{trt,high})]}$$

7.4.1.2. Sensitivity Analysis of Nonrelapse Mortality Rate at Month 6 (Day 180) Using Kaplan-Meier Approach

A sensitivity analysis will also be conducted where NRM at Day 180 will be estimated by 1 minus the survival probability at Day 180 using the KM estimator.

A stratified test statistic for NRM rate at Day 180 is proposed as:

$$TS_{Day180NRM} = \frac{\left[\sum_{j=1}^2 (\widehat{CDF}_{pbo,j}(t=D180) - \widehat{CDF}_{trt,j}(t=D180)) \right]^2}{\sum_{j=1}^2 Var(\widehat{CDF}_{pbo,j}(t=D180) - \widehat{CDF}_{trt,j}(t=D180))}$$

$$= \frac{\left[\sum_{j=1}^2 (\widehat{CDF}_{pbo,j}(t = D180) - \widehat{CDF}_{trt,j}(t = D180)) \right]^2}{\sum_{j=1}^2 (SE(\widehat{CDF}_{pbo,j}(t = D180))^2 + SE(\widehat{CDF}_{trt,j}(t = D180))^2)}$$

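### SAP 3.3 names two different tests for the alpha-controlled Month 6 NRM comparison, contradicts SAP 7.4.1 by doing so, and does not say which test its power figure belongs to

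*SAP*

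**What the plan says.** Five places bear on how Month 6 (Day 180) NRM is tested.

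- **SAP 3.3, Sample Size Considerations:** "The Day 180 NRM rate difference between 2 groups is tested using a KM estimator of the cumulative distribution function at Day 180". Later in the same paragraph: "NRM at Month 6 will be tested using a CMH test stratified by risk status". Neither sentence is qualified.
- **SAP 7.4.1.1:** "For the primary analysis, NRM will be analyzed using a stratified CMH test". SAP 7.4.1 and 7.4.1.2 label the KM estimate and its test as sensitivity analyses.
- **SAP 9.1.2:** the Interim 2 analysis of NRM uses the method of Section 7.4.1, as at the final analysis.
- **Protocol 9.4.2:** "The comparison of NRM at Month 6 between treatment cohorts will be conducted using a 2-sample proportion test with normal approximation". No stratification is mentioned.
- **Protocol 9.2:** NRM is powered with a two-stratum CMH test (83% with 414 subjects). KM enters only conditionally: "If the Day 180 NRM rate difference between 2 groups is tested using a Kaplan–Meier estimator", followed by a simulated power of 0.811 with 436 subjects.

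SAP 10.1, the section for changes to Protocol-defined analyses, mentions only the name of the analysis population. SAP 10.2.1 records that the definition and analysis of Month 6 NRM were refined after health authority feedback, but not which test replaced which.

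On power, SAP 3.3 gives about 80% with 414 subjects and attributes it to simulation. It then says that power for the CMH test came from N-Query. On alpha, SAP 3.3 says "the key secondary endpoint (NRM rate at Month 6) will be tested at 1-sided" 0.025, whereas SAP 3.4.2 and 9.1.2 use "0.0125 as compared with 1-sided p-value at both interim and final analyses".

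**The concern.** Month 6 NRM is the only endpoint besides Day 28 ORR under type I error control (SAP 3.2), and stopping for efficacy at Interim 2 requires both boundaries to be crossed (SAP 3.4). The rule for such an endpoint should name one statistic wherever it appears. Here a programmer or assessor working from SAP 3.3 could take the KM difference as the deciding test, and one working from Protocol 9.4.2 could take the unstratified proportion test. Nothing in the SAP states that 7.4.1 overrides 3.3.

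The power statement has the same fault. If the figure of about 80% describes the KM test, the SAP gives no power for the CMH test that decides the endpoint.

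**Working it through.** **Inputs.** From SAP 3.3: control NRM 22% (standard risk) and 44% (high risk); itacitinib 12.4% and 28.2%; strata 50:50; 207 per arm, so n = 103.5 per arm per stratum. The overall effect is given as an "absolute difference of 13.2%, ie, 19.8% vs 33% at Day 180"; the stratum rates for itacitinib average (12.4 + 28.2)/2 = 20.3%. I use the stratum rates. One-sided critical values are 1.960 (0.025) and 2.241 (0.0125).

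**Step 1: reproduce the Protocol's 83% for CMH.** Power = Φ[(D − z√V0)/√V1].
- D = (n/2) × Σ(p0 − p1) = 51.75 × (0.096 + 0.158) = 13.14.
- V0 (hypergeometric, with stratum averages 0.172 and 0.361) = 103.5²/206 × (0.1424 + 0.2307) = 19.40; √V0 = 4.405.
- V1 = (n/4) × Σ[p0(1 − p0) + p1(1 − p1)] = 25.875 × 0.7291 = 18.87; √V1 = 4.343.
- At 0.025: (13.14 − 1.960 × 4.405)/4.343 = 1.039, power 85.0%. With a continuity correction of 0.5: 0.924, power 82.2%.

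The corrected version agrees with 83% to within a point, so 83% is a CMH figure at 0.025.

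**Step 2: the same test at 0.0125.** (13.14 − 2.241 × 4.405)/4.343 = 0.753, power 77.4% (73.8% with continuity correction). With 218 per arm and no correction, power is 86.8% at 0.025 and 79.8% at 0.0125.

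**Step 3: the KM statistic of SAP 7.4.1.2 without censoring.** Sum of stratum differences = 0.254; variance = 0.7291/103.5 = 0.00704; SE = 0.0839; ratio = 3.026.
- At 0.025: Φ(3.026 − 1.960) = 85.7%.
- At 0.0125: Φ(3.026 − 2.241) = 78.4%.
- With 436 subjects: 87.4% and 80.6%.

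**Step 4: trace the SAP's figure of about 80%.** In Protocol 9.2 the simulated figure (0.811) is for KM and the CMH figure is 83%. A simulated value near 80% therefore looks like the KM test, but the inputs to the simulation are not given. At 0.025, KM power falls to about 80% only with assumed withdrawal of roughly 10-20% plus 10% relapse death by Day 180. At 0.0125 it is close to 80% with no censoring at all. The documents do not settle which applies.

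**Step 5: does the choice of test change the verdict?** The tests were simulated on the same data sets, 218 per arm, at one-sided 0.0125. The documents give no relapse-death or withdrawal rates by Day 180, so these are assumptions.

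| Assumed censoring by Day 180 | CMH and KM verdicts differ |
|---|---|
| None | about 0.5% of trials |
| Relapse death 5-10%, withdrawal 2-10% | about 2-4% |
| Relapse death 20%, withdrawal 20% | 7.9% |

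In the first two rows the two tests' powers are within about 0.6 points of each other.

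**Step 6: a worked borderline case.** 109 subjects per cell, complete follow-up, NRM deaths 24 and 48 on placebo, 15 and 36 on itacitinib.
- CMH: (4.5 + 6.0)/√(8.04 + 12.97) = 10.5/4.584 = 2.291, p = 0.0110.
- KM: (21/109)/0.0834 = 2.310, p = 0.0104.
- Two-sample: (72 − 51)/218 = 0.0963; pooled rate 123/436 = 0.282; SE 0.0431; z = 2.235, p = 0.0127.

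At 0.0125 the first two pass and the third fails. All three use the same subjects here, so the denominator plays no part.

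**The case against.** The strongest reply is that the operative sections already settle the matter. SAP 7.4.1.1 is the section headed as the primary NRM analysis and names stratified CMH. KM is twice called a sensitivity analysis. SAP 9.1.2 carries the 7.4.1 method to Interim 2, and the second sentence in SAP 3.3 agrees. The KM sentence sits in a sample-size section and resembles the conditional sentence in Protocol 9.2, so it may be leftover power text, though that is an inference. The two-sample test appears only in the Protocol, and Protocol 9.2 itself plans CMH. SAP 10.2.1 did announce a change to the NRM analysis. All of this stands.

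It disposes of a tempting stronger reading: that three tests are equally admissible, so the deciding one could be picked after the data are seen and type I error inflated accordingly. SAP 7.4.1.1 and 9.1.2 exclude that choice.

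A reader might also note that SAP Amendment 1 (23 JUL 2019) postdates the Interim 2 data cutoff (17 APR 2019, SAP 5.3.2) and infer that the test was chosen with knowledge of results. The documents do not support this. SAP 9.1.2 says the sponsor stays blinded, and the change log attributes the change to health authority feedback.

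Nor should every disagreement between tests be put down to the statistic. The SAP's CMH analysis leaves out relapse deaths and early withdrawals, KM censors them, and Protocol 9.4.2 does not say how they are handled. Part of any difference under censoring comes from these denominators.

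The reply does not remove the unqualified KM sentence, the unlisted departure from Protocol 9.4.2, or the doubly attributed power.

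**Conclusion.** The inconsistency is real and should be corrected, but it is limited. The SAP read as a whole makes stratified CMH the deciding test at Interim 2 and at the final analysis. SAP 3.3 contradicts this in one sentence, Protocol 9.4.2 names a different test, and SAP 10.1 is silent on the change. The stated power of about 80% cannot be assigned to the deciding test from the documents.

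The practical effect of the CMH/KM conflict is small: different verdicts in about 0.5% of trials without censoring and about 2-4% with moderate assumed censoring, at one-sided 0.0125. Those figures rest on the plan's stratum rates and 50:50 split and on assumed relapse-death and withdrawal rates; heavier censoring raises them.

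The separate disagreement over alpha matters more for power. Moving CMH from 0.025 to 0.0125 costs 85.0 − 77.4 = 7.6 points, which is why the restated power must name its alpha.

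**What to change.** 1. In SAP 3.3, delete the KM sentence or relabel it as describing the sensitivity analysis of 7.4.1.2.
2. State in SAP 3.3 that the stratified CMH test of 7.4.1.1 is the sole alpha-controlled test of Month 6 NRM, at Interim 2 and at the final analysis.
3. Give the power of that CMH test at the alpha actually used. Without censoring or continuity correction at 207 per arm this is about 85% at one-sided 0.025 and about 77% at 0.0125. Label any simulated figure as KM, with its alpha and censoring assumptions.
4. In SAP 10.1, record that stratified CMH replaces the two-sample proportion test of Protocol 9.4.2.

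The cost is SAP wording and one restated power figure. Design, sample size and data collection are unaffected.

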3.4. Interim and Final Analyses

There are 2 interim analyses planned in this study. Interim Analysis 1 will be conducted at the time when 112 subjects have completed the Day 28 visit or withdrawn from the study. Only a futility analysis will be conducted based on test statistic of Day 28 ORR using stratified CMH test (see details below). The observed normalized z statistic will be compared with the futility boundary of 0.626 as depicted in Figure 3 (equivalently conditional power equal to 0.2); if the normalized z statistic is less than the futility boundary, it is recommended to stop the study early for futility. Interim Analysis 2 will be conducted when approximately 240 subjects have completed the Day 180 visit or have withdrawn from the study. At Interim Analysis 2, both futility and efficacy will be tested for Day 28 ORR using stratified CMH test with z-score efficacy boundary of 2.25 and futility boundary of 1.46 corresponding to conditional power of 0.2. Critical value at final analysis is 2.02. See details on boundary specifications in Sections 3.4.1 and 3.4.2. Note that boundaries for both the Interim Analysis 2 and the Final Analysis are constructed based on a hypothetical example solely for illustration purposes, whereas the real boundaries used in the study will be based on the observed information fraction at Interim Analysis 2.

Figure 3: Upper Efficacy and Lower Futility Boundaries for Day 28 ORR at the Interim Analyses and Critical Value at the Final Analysis

In any interim analysis, the sponsor may consider stopping the study for futility if the conditional power is less than 20% and stopping for efficacy if both efficacy boundaries are crossed. If neither the efficacy nor the futility boundary for Day 28 ORR is crossed, the study will continue. Additionally, if efficacy for Day 28 ORR is crossed but efficacy for Day 180 NRM rate is not crossed, the study will continue.

3.4.1. Interim Analysis 1

The first interim analysis for futility only will be performed when 112 subjects (25.7% of the planned 436 subjects) have completed the Day 28 visit or withdrew early from study. No alpha will be spent during the first interim analysis. The stopping rule is nonbinding. When the conditional power is < 20%, the sponsor may consider terminating the study if the totality of evidence is warranted. The conditional power is calculated assuming that the estimated treatment effect at the interim analysis is the true effect using the formula (Jennison and Turnbull 1999):

$$\Phi \left(\frac{z}{\sqrt{t(1-t)}} - \frac{z_{\alpha/2}}{\sqrt{1-t}} \right)$$

where Φ is the cumulative distribution function of the observed normalized test statistic z , and t is the information fraction (ie, observed sample at interim divided by the planned total sample size 436); $t = 0.257$ at Interim 1 and $z_{\alpha/2} = 1.96$.

Since CMH test with only 1 stratification factor, aGVHD risk status (standard vs high risk), will be used to test ORR at Day 28, it is thus a chi-square test with degree of freedom equal to 1, that is, $\chi^2_{df=1}$. Taking the square root of the observed CMH test statistic $\chi^2_{df=1}$ will result in normalized test statistic z .

3.4.2. Interim Analysis 2

For Interim Analysis 2, the analysis of both efficacy and futility will use a clinical database cutoff based on when 240 eligible subjects (55.0% of the targeted 436 subjects) have completed the Day 180 visit or withdrew from the study prior to Day 180.

The Hwang-Shih-DeCani alpha spending function with shape parameter -4 (O'Brian-Fleming like boundary) will be used to define upper efficacy boundary for the primary analysis of ORR at Day 28 when approximately 240 eligible subjects reach Day 180 (Hwang et al 1990). Based on enrollment projection, there will be approximately 360 subjects who have completed Day 28.

Table 2 lists efficacy boundary when information fraction (ie, the percentage of subjects) is 0.826 (360 subjects complete Day 28) at Interim 2; if ORR tested at Day 28 crosses the boundary, then the key secondary endpoint, 6-month NRM rate, will be tested by using the Bonferroni method for alpha spending (ie, 0.0125 as compared with 1-sided p-value at both interim and final analyses). By simulation, without considering early stopping for futility, the power of testing 6-month NRM at Interim 2 (with 240 eligible subjects who have completed Day 180) is approximately 0.608.

Table 2: Operation Characteristics Using Hwang-Shih-DeCani Alpha Spending Function With Shape Parameter -4

		No. of Subjects (%)	Alpha Spent /Cumulative	Efficacy Boundary or Critical Value (as Compared With Observed Normalized Test Statistic z)	Nominal Significance /Alpha Level: $1 - \Phi(d)$	Efficacy Boundary or Critical Value at Chi-Square Test Statistic With Degree of Freedom 1
ORR at Day 28	Interim Analysis 1	112 (25.7)	–	–	–	–
	Interim Analysis 2	360 (82.6)	0.0122/0.0122	2.249810	0.0122305	5.061645
	Final	436 (100)	0.0128/0.025	2.015483	0.02192703	4.062172

If, at Interim Analysis 2, the observed number of subjects who have completed Day 28 is different from 360, then the boundaries for efficacy in [Table 2](#) will be recalculated using observed information fraction.

The interim analyses will be performed by an independent statistician and programmer not involved with the conduct of the study as described in the DMC charter.

At the Interim Analysis 2 clinical data cutoff date, the date when the 240th eligible subject randomized in the study has reached Day 180, 360 subjects are expected to have been randomized. Testing of Day 28 ORR will be conducted for subjects who have completed the Day 28 visit or withdrew from the study by the clinical data cutoff date. This means that subjects who were ongoing but had not yet reached the Day 28 visit by the Interim Analysis 2 clinical data cutoff date will be excluded from both the Day 28 ORR and NRM efficacy analyses.

[Figure 4](#) depicts the recommended decision process at Interim Analysis 2: first, testing Day 28 ORR using stratified CMH and assuming 360 subjects have completed Day 28 or withdrew from the study by the cutoff date, if observed normalized test statistic is ≤ 1.46 , it is recommended to stop the study for futility; if the observed normalized test statistic of Day 28 ORR is ≥ 2.25 , then the NRM rate at Day 180 will be tested using the Bonferroni method. If both the primary efficacy analysis and the key secondary efficacy analysis pass their corresponding efficacy boundary, the superiority of itacitinib over placebo for both the Day 28 ORR and Day 180 NRM endpoints can be claimed at Interim Analysis 2.

Table 3: Schedule of Assessments

Visit Day Item	Screening -28 to -1	Treatment ^a												EOT ^d	Retreatment ^e	Follow-Up		
		D1	D7	D14	D21	D28	D35	D42	D49	D56 ^b	D100	D180	D365 ^c			Safety ^f	GVHD ^g	Survival ^h
Informed consent	X																	
I/E criteria	X	X																
Contact IVRS	X	X					X				X	X		X	X	X		
Demography/disease history	X																	
Prior/concomitant medications	X	X												X	X	X		
Supportive care medications	X	X												X	X	X		
AE assessment	X	X												X	X	X		
Physical examination	X	X	X	X	X	X	X	X	X	X	X		X	X	X	X		
Vital signs	X	X	X	X	X	X	X	X	X	X	X		X	X	X	X		
ECOG PS	X	X	X	X	X	X	X	X	X	X	X		X	X	X	X		
12-lead ECG	X	As indicated												X				
aGVHD grading and response	X	X	X	X	X	X	X	X	X	X	X	X	X	X	X	X	X	
cGVHD assessment	X	As indicated												X	X	X	X	
Chimerism/graft failure assessment	X	As indicated																
PTLD assessment		As indicated												X	X	X	X	
Underlying disease relapse assessment		As indicated												X	X	X	X	X
Dispense study drug		X				X				X			X		X			
Study drug compliance		X				X				X			X	X	X			
Steroid dose monitoring	X	X												X	X			
Survival follow-up																		X
New aGVHD therapies																		X

ECG = electrocardiogram; I/E = inclusion/exclusion; PS = performance status; PTLD = post-transplant lymphoproliferative disorder.

^a A ± 3-day window is permitted to facilitate scheduling during the treatment phase.

^b After Day 56, visits will occur every 28 days and will include all Day 56 assessments.

^c The Day 365 visit will also serve as the regularly scheduled visit occurring every 28 days after Day 56 (ie, Day 364).

^d A second EOT should occur if the subject restarts itacitinib and subsequently discontinues treatment.

^e Retreatment assessments occur every 28 days ± 3 days.

^f 30 to 35 days after EOT.

^g Every 28 days ± 7 days, for participants who completed study treatment or discontinued early for reasons other than GVHD progression.

^h Every 8 weeks ± 7 days.

Table 4: Laboratory Assessments

Visit Day Item	Screening	Treatment ^a											EOT ^e	Retreatment ^f	GVHD Follow-Up	Safety Follow-Up ^g	
	-28 to -1	D1 ^b	D7	D14	D21	D28	D35	D42	D49	D56 ^c	D100	D180					D365 ^d
Chemistry panel	X	X	X	X	X	X	X	X	X	X	X		X	X	X	X ^h	X
Hematology	X	X	X	X	X	X	X	X	X	X	X		X	X	X		X
Hepatitis screening	X																
HIV screening	X																
Serum pregnancy test (childbearing females only)	X													X			
Urine pregnancy test ⁱ (childbearing females only)						X				X							
PK assessment ^j		X	X			X											

^a A ± 3-day window is permitted to facilitate scheduling during the treatment phase.
^b Day 1 laboratory assessments do not need to be repeated if screening assessments were performed within the preceding 7 days.
^c After Day 56, visits will occur every 28 days and will include all Day 56 assessments.
^d The Day 365 visit will also serve as the regularly scheduled visit occurring every 28 days after Day 56 (ie, Day 364).
^e A second EOT should occur if the subject restarts itacitinib and subsequently discontinues treatment.
^f Retreatment assessments occur every 28 days.
^g 30 to 35 days after EOT.
^h Liver testing including total bilirubin data
ⁱ Urine pregnancy tests are required at Day 28 and every 28 days.
^j Subjects 1-112: samples collected on Days 1, 7, and 28 at predose and at 1 hour ± 15 minutes, 2 hours ± 30 minutes, and 5 hours ± 60 minutes postdose. Subjects 113-436: Day 7 and 28 at predose only.
^k Day 56 only.

Table 5: Clinical Laboratory Analytes

Serum Chemistries	Hematology ^a	Other
Albumin ALP ALT AST Bicarbonate or CO ₂ Blood urea nitrogen Calcium Chloride Creatinine Glucose Lactate dehydrogenase Lipid profile (total cholesterol, HDL, LDL, and triglycerides) Phosphorus Potassium Sodium Total bilirubin Total protein	Hematocrit Hemoglobin Mean corpuscular volume Reticulocytes Platelet count Red blood cell count White blood cell count White blood cell differential (5 parts): 
 • Basophils • Eosinophils • Lymphocytes • Monocytes • Neutrophils 	Serum pregnancy test Urine pregnancy test Hepatitis Screening Tests Hepatitis B surface antigen Hepatitis B surface antibody Hepatitis B core antibody HCV antibody HCV-RNA HBV-DNA

ALP = alkaline phosphatase; ALT = alanine aminotransferase; AST = aspartate aminotransferase;

HDL = high-density lipoprotein; LDL = low-density lipoprotein.

^a Hematology and chemistry assessments will be performed locally.

